**Feeling and Body Investigators for Pediatric Abdominal Pain (FBI)**

**NCT02075437**

**01/28/2019**

### **Primary Outcome 1. Percentage of Participants Who Complete Treatment**

Participants were considered to have completed treatment if they completed all 10 treatment sessions.

### **Primary Outcome 2. Percentage of Participants Completing Homework Assignment**

As part of the study, participants were asked to complete homework assignments after each treatment session. These assignments consisted of weekly pain diaries, which included both parent reports of child experience and child reports of their own experience of different types of pain. At pre-treatment and post treatment these parent and child ratings were completed three times daily (beginning of day, before dinner, and end of day), with the end of day assessments asking about the worst pain that day and the others assessing pain at that moment. For homework assignments given during treatment sessions, participants were asked only to report at one time point (end of day) daily.

- In assessing participants' completion rate of their homework assignments all pain diaries were entered into a singular database, and reverified to ensure data quality control. Once all data was collected, all weekly pain diaries were assessed for completion and given a label indicating their level of completion, the labels and criteria are described below.

Label	Meaning
Complete	Participant completed all days of the end of day diary packet
Complete Partial	Participant completed 4 or more days of the end of day diary packet
Incomplete Partial	Participant completed 3 or less days of the end of day diary packet
Not Completed	Participant did not complete any days in the end of day diary packet
Not Given	Participant not given end of day diary packet

- For our analysis, if a participant completed at least 1 pain diary entry in a weekly pain diary they were considered as having successfully completed their homework assignment for that given week.
- Once all participant labeling was completed percentages of completion rates were calculated by dividing the number of homework completions by the number of homework assignments given. Those with a completion percentage of equal or greater than 90% were then considered to be "successful".

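### SAP Primary Outcome 2 counts a weekly diary as completed on a single entry, although its own label table grades 1 to 3 days as incomplete, and no result on the stricter cut is planned

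*SAP*

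**What the plan says.** The SAP, under Primary Outcome 2, treats weekly pain diaries as the homework: "participants were asked to complete homework assignments after each treatment session". During treatment the diary has one time point per day, at the end of the day. Each packet receives one of five labels:

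- *Complete*: every day filled.
- *Complete Partial*: at least 4 days filled.
- *Incomplete Partial*: "Participant completed 3 or less days of the end of day diary packet". Zero days has its own label, so this means 1 to 3 days.
- *Not Completed*: "Participant did not complete any days in the end of day diary packet".
- *Not Given*: no packet was handed out.

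The weekly rule follows: "if a participant completed at least 1 pain diary entry in a weekly pain diary they were considered as having successfully completed" the assignment for that week. The participant's rate is obtained by "dividing the number of homework completions by the number of homework assignments given". The final step is: "Those with a completion percentage of equal or greater than 90% were then considered to be" successful.

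The SAP gives no reason for the one-entry cut and no analysis on a stricter one. The protocol's Statistical Methods section does not address it either.

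The protocol describes homework differently. Its Feasibility paragraphs (R21 and R33) have therapists record home practice at each session. Practice sessions are counted however fully they were done, and in the same sentence quality is graded as none, attempt or completed. The R33 hypothesis HB1b sets a target of at least 80% of participants for homework.

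**The concern.** The label table and the analysis rule disagree on what an incomplete week is. A week that the table grades as incomplete earns the same credit as a week with every day filled. The three non-zero labels are therefore interchangeable in the analysis, and the only distinction that matters is zero against not zero.

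This is one of only two primary outcomes in the SAP, and it is the one that measures homework feasibility. Someone who reads a percentage of participants completing homework would expect more than one diary day a week. If families often fill in only a few days, the reported figure would describe minimal contact with the diary rather than completion, and the report would contain nothing to show the difference.

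**Working it through.** The documents state no minimum-adherence figure for this outcome, so there is none to reproduce. The rule's implications can be counted directly.

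**1. Which labels pass.** Under the one-entry rule *Complete*, *Complete Partial* and *Incomplete Partial* pass and *Not Completed* fails. *Not Given* is outside the denominator. The 4-day boundary has no effect.

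**2. Minimum share of entries for a successful participant.**

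Inputs: success at 90% or more of packets given (SAP); 10 sessions with homework after each (SAP); one end-of-day entry per day during treatment (SAP); 7 days per packet (assumed from the 7-day diaries in the protocol's Assessment Procedures).

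With n packets and at least c days needed per week, the packets needed are r = ceil(0.9n), and the minimum share is r × c / (7n). For n = 10, r = 9:

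- c = 1 (SAP rule): 9/70 = 12.9%
- c = 4 (*Complete Partial* or better): 36/70 = 51.4%
- c = 7 (*Complete* only): 63/70 = 90.0%

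The packet count is uncertain, because the protocol's Pain paragraph has ratings in only 2 of the 10 treatment weeks. With n = 2 the first two minimums are 2/14 = 14.3% and 8/14 = 57.1%. With n = 12 they are 11/84 = 13.1% and 44/84 = 52.4%. For any n from 1 to 12 the one-entry minimum lies between 12.9% and 14.3%, so this doubt does not change the point.

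**3. How far apart the two rules could be.** This step is illustrative and every adherence input is assumed. A family's daily completion probability p follows a Beta distribution with mean μ and intraclass correlation (ICC) ρf, with parameters μ(1−ρf)/ρf and (1−μ)(1−ρf)/ρf. Given p, days filled in a week are beta-binomial(7, p) with week ICC ρw, or binomial if ρw = 0. Let q be the probability that a week has at least c days. With 10 packets,

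P(successful) = average over p of [q^10 + 10·q^9·(1−q)].

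The table shows the percentage successful under the one-entry rule vs the 4-day cut. In each cell the first line is family ICC 0.1 and the second is 0.3.

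| Daily completion | Week ICC 0 | 0.3 | 0.6 | 0.9 |
|---|---|---|---|---|
| 30% | 62.7 vs 1.7<br>51.0 vs 11.2 | 24.2 vs 0.8<br>29.6 vs 6.7 | 6.6 vs 0.6<br>15.1 vs 5.3 | 1.2 vs 0.6<br>6.6 vs 4.9 |
| 50% | 93.0 vs 17.0<br>78.3 vs 31.2 | 62.3 vs 8.1<br>56.9 vs 21.0 | 28.4 vs 6.0<br>36.1 vs 17.4 | 8.7 vs 5.4<br>20.1 vs 16.4 |
| 70% | 99.5 vs 59.0<br>93.3 vs 60.2 | 90.1 vs 35.7<br>80.8 vs 46.9 | 63.5 vs 28.0<br>63.1 vs 41.5 | 33.5 vs 25.9<br>44.9 vs 39.9 |
| 90% | 100 vs 95.3<br>99.1 vs 89.3 | 99.2 vs 83.1<br>96.0 vs 82.2 | 93.2 vs 76.2<br>89.6 vs 78.7 | 79.4 vs 73.9<br>80.6 vs 77.6 |

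Adding family ICC 0.2 gives 4 × 4 × 3 = 48 scenarios. Across them:

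- The gap runs from 0.6 to 76.1 points.
- It is below 8 points in every scenario with week ICC 0.9.
- It exceeds 70 points in one scenario only: 50% daily completion, independent days, family ICC 0.1.
- The rules fall on opposite sides of 80% in 12 scenarios. Both reach 80% in 6 and both miss it in 30. With 2, 8 or 12 packets the split count is 9, 8 or 12 of 48.

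These counts depend on the grid chosen and are not probabilities.

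**The case against.** The best defence has four parts.

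**The rule is open.** The SAP says exactly what was counted, the outcome is a feasibility measure, and no between-arm test on it is specified. That stands, and nothing here suggests concealment. Disclosure does not explain why the SAP's own grading was set aside, though, or show what the choice does to the figure.

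**There is a precedent.** The protocol's Feasibility paragraphs count homework frequency whatever the degree of completion, so it would be wrong to say that the documents offer no support for lenient counting. The support is partial: it concerns practice sessions, and it sits beside a quality grade that the SAP outcome drops.

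**The 90% participant threshold is demanding.** It is demanding about the number of weeks but not about what a week must contain, and the 12.9% minimum already includes it. It does mean that the rule guarantees no favourable result: in 30 of the 48 scenarios both rules miss 80%.

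**Families may fill or skip a booklet as a unit.** The diary is a paper booklet handed in afterwards (protocol, Assessment Procedures), so strong within-week correlation is plausible. The gap would then be small. This cannot be settled without the label distribution.

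Three stronger readings are tempting and not supported. A reader might infer that the reported percentage is inflated by 70 points or more, but that needs one corner of the grid and no adherence data are given. A reader might infer that the one-entry rule decides whether HB1b is met, but the protocol describes homework as home practice while the SAP scores diaries, and the SAP names neither HB1b nor 80%. A reader might take "Once all data was collected, all weekly pain diaries were assessed for completion" to mean that the cut was chosen after seeing the data. That sentence dates the labelling, not the choice of rule.

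**Conclusion.** The inconsistency is real and rests on the SAP text alone: weeks graded incomplete are counted as successfully completed in a primary outcome named for completion, and the 4-day cut goes unused. The minimum adherence compatible with success is 12.9% of entries, given 10 packets of 7 days with one scored entry per day, and 12.9% to 14.3% for 1 to 12 packets. On the 4-day cut it would be 51.4% with 10 packets. These are worst cases derived from the rule; they do not describe any participant.

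The effect on the reported percentage is unknown. It could be negligible or large, depending on daily adherence and on how strongly days cluster within weeks and families. The documents do not show that the result is wrong. They show that it cannot be read as completion without a second figure beside it.

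**What to change.** Keep the stated rule and its result, name it as any diary entry, and give the reason for it. Beside it report:

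- the participant-level success rate (same 90% threshold) counting only *Complete* and *Complete Partial* weeks;
- the distribution of all five labels, including *Not Given*, which also shows how many packets participants received;
- the percentage of assigned diary days completed.

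Mark these additions as post hoc if the data were already collected. Do not describe homework as completed on the any-entry rate alone if the 4-day result does not support it. If the result is set against the protocol's 80% homework target, apply the comparison to both rates and state that the protocol describes homework as home practice whereas the SAP scores diaries.

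The SAP says that every weekly diary was labelled, so this needs no new data and leaves the primary definition unchanged. The cost is some SAP wording, one extra table, and possibly a less favourable completion figure next to the primary one.
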